###### **Contraceptive Methods with a Failure Rate of <1%**

- Combined hormonal contraception associated with inhibition of ovulation (oral, intravaginal, transdermal).
- Progestogen-only hormonal contraception associated with inhibition of ovulation (oral, injectable, implantable).
- Intrauterine device (IUD) or intrauterine system (IUS) that meets the <1% failure rate as stated in the product label.

- Male partner sterilization (vasectomy with documentation of azoospermia) prior to the female participant's entry into the study, and this male is the sole partner for that participant. For this definition, “documented” refers to the outcome of the investigator's/designee's medical examination of the participant or review of the participant's medical history for study eligibility, as obtained via a verbal interview with the participant or from the participant's medical records.
- Female participants and female partners of male study participants using a hormonal contraceptive must also use a barrier method (i.e., condom or occlusive cap [diaphragm or cervical/vault caps]) and should have been stable on their hormonal contraceptive treatment for at least 4 weeks before Screening.
- Sterilized male participants who have had vasectomy with documented azoospermia post procedure can be included.
- Non-sterilized male participants who are sexually active with a female partner of childbearing potential must use effective method of double barrier contraception. Male participants practicing true sexual abstinence (when this is in line with the preferred and usual lifestyle of the participant) can be included. In addition, male participants must be advised not to donate sperm during this period from signing of Informed Consent Form (ICF), throughout the duration of the study, and for 90 days after the last administration of study drug.

These allowed methods of contraception are only effective when used consistently, correctly and in accordance with the product label. The investigator is responsible for ensuring participants understand how to properly use these methods of contraception.

Participants must be completely informed of the unknown risks of pregnancy and agree not to become pregnant during the time they are participating in this study. If there is any question that a participant will not be reliable in the use of appropriate contraceptive methods, they should not be entered into the study.

## **6.8. Withdrawal Criteria**

### **6.8.1. Reasons for Withdrawal**

A Principal Investigator may discontinue/withdraw a study participant's participation in the study if any of the following criteria apply:

- Any clinical AE, laboratory abnormality, or other medical condition or situation occurs such that continued participation in the study would not be in the best interest of the participant.
- Participant pregnancy
- Significant protocol violation
- Behavioral or administrative reason

- Participant request to discontinue/withdraw consent for any reason. It is important to document whether the withdrawal of consent is primarily due to an AE, lack of efficacy, or other reason.
- Discontinuation of the study at the request of the Sponsor, regulatory agency or an Institutional Review Board / Independent Ethics Committee
- Stopping criteria, as noted in Section 6.9

If a participant meets a withdrawal criterion during treatment, an Early Termination visit will be required (Section 6.7.2).

### **6.8.2. Participant Withdrawal Procedures**

If a participant is prematurely discontinued from the study, the Principal Investigator must make every effort to perform an Early Termination Visit per Section 8.1 and Section 8.2, Time and Events Tables and document the primary reason for withdrawal.

Should a participant fail to attend the clinic for a required study visit, the site should attempt to contact the participant and re-schedule the missed visit as soon as possible. The site should also counsel the participant on the importance of maintaining the assigned visit schedule and ascertain whether or not the participant wishes to and/or should continue in the study based on previous non-compliance. In cases where the participant does not return for the rescheduled visit or cannot be reached to reschedule the missed visit, the site should make every effort to regain contact with the participant (3 documented telephone calls and if necessary a certified letter to the participant's last known mailing address) so that they can appropriately be withdrawn from the study with a primary reason of "Lost to Follow-up".

## **6.9. Stopping Criteria for Individual Participants**

### **6.9.1. Liver Chemistry Stopping Criteria**

Hepatic enzymes will be monitored in accordance with FDA drug-induced liver injury guidelines [FDA, 2009].

If the following liver test abnormalities develop, Study Treatment should be withheld immediately with appropriate clinical follow-up (including repeat laboratory tests, until a participant's laboratory profile has returned to normal/baseline status), and the event reported as a SAE:

- Alanine aminotransferase (ALT) or aspartate aminotransferase (AST)> 8 x upper limit of normal (ULN); or
- ALT or AST > 5 x ULN and persists for more than 2 weeks; or
- ALT or AST > 3 x ULN and total bilirubin > 2 x ULN or international normalized ratio (INR) > 1.5

- ALT or AST  $> 3 \times$  ULN with appearance of fatigue, nausea, vomiting, right upper quadrant pain or tenderness, fever, rash and/or eosinophilia ( $> 5\%$ ).

Rechallenge may be considered if an alternative cause for the abnormal liver tests (ALT, AST, total bilirubin) is discovered and the laboratory abnormalities resolve to normal or baseline values. The Investigator and sponsor must discuss and agree with any decision to rechallenge.

Rechallenge should not occur when the etiology of the liver test abnormalities is considered possibly drug induced.

#### **6.9.2. Criteria for Permanent Discontinuation of Study Treatment in Association with Liver Test Abnormalities**

Study treatment should be discontinued permanently if all of the following 4 criteria are met (i.e., potential severe drug-induced liver injury/Hy's law case):

[figure not shown]
1. Total bilirubin increases to  $> 2 \times$  ULN or INR  $> 1.5$ ; AND
2. AST or ALT increases to  $\geq 3 \times$  ULN; AND
3. Alkaline phosphatase value does not reach  $2 \times$  ULN; AND
4. No alternative cause explains the combination of the above laboratory abnormalities; important alternative causes include, but are not limited to the following:
  - Hepatobiliary tract disease;
  - Viral hepatitis (e.g., hepatitis A/B/C/D/E, Epstein-Barr virus);
  - Exposure to hepatotoxic agents/drugs or hepatotoxins, including herbal and dietary supplements, plants, and mushrooms;
  - Alcoholic hepatitis;
  - Non-alcoholic steatohepatitis; or
  - Autoimmune hepatitis.

If an alternative cause for hepatotoxicity is identified, then it should be determined (based on the severity of the hepatotoxicity or event) whether Study Treatment should be withheld or permanently discontinued as appropriate for the safety of the participant.

#### **6.9.3. QTc Withdrawal Criteria**

- QTc prolongation defined as QTcF  $> 500$  ms, or an increase of QTcF  $> 60$  ms above baseline on the 12-lead ECG, confirmed (persistent for  $> 5$  minutes) on repeated 12-lead ECGs

#### 6.9.4. **Albumin Monitoring Criteria**

## 6.10. Toxicity Management Criteria

### 6.10.1. Toxicity Management Criteria (AEs, Cardiovascular, and Site Reactions)

The severity of each AE will be graded and managed according to the criteria in Table 1.

**Table 1 Criteria for Determining the Grade/Severity of Adverse Event Terms**

Grade	Criteria
1/Mild	Asymptomatic or mild symptoms, clinical or diagnostic observations only; intervention not indicated
2/Moderate	Limiting age-appropriate instrumental activities of daily living; minimal, local, or noninvasive intervention as indicated
3/Severe or medically significant	Not immediately life-threatening; hospitalization or prolongation of hospitalization indicated; disabling; limiting self-care activities of daily living, intervention as indicated
4/Life-threatening	Life threatening consequences; urgent intervention indicated
5/Death	Death related to adverse event

### Injection Site Reactions

Injection site evaluations will be made by clinical staff following administration of RVT-1401 and placebo as described below. Additional details related to the specific injection site location will be included within a study specific manual. If an injection site reaction is observed, a physician will characterize and document the reaction as an AE. Review of the injection site will continue until the AE is resolved. Symptomatic treatment (e.g. antihistamines, NSAIDs, IV fluids) may be provided for any injection site reactions based on the discretion of the Investigator.

The injection sites will be monitored for pain, tenderness, erythema and swelling. Each injection site reaction will be categorized using the intensity grading scheme presented in Table 2.

**Table 2 Criteria for Determining the Grade/Severity of Injection Site Reactions**

Grade	Criteria
1/Mild	Tenderness with or without associated symptoms (e.g., warmth, erythema, itching)
2/Moderate	Pain; lipodystrophy; edema; phlebitis
3/Severe or medically significant	Ulceration or necrosis; severe tissue damage; operative intervention indicated
4/Life-threatening	Life threatening consequences; urgent intervention indicated
5/Death	Death

Common Terminology Criteria for Adverse Events (CTCAE) Version 4.0 Published: May 28, 2009 (v4.03: June 14, 2010).

### **6.10.2. Other Management Criteria**

For an individual study participant, medical monitor notification criteria include, but are not limited to:

- Severe signs or symptoms, or significant changes in any of the safety assessments, that put the safety of the individual at risk (e.g. laboratory tests or vital signs, etc.) as judged by the Investigator.

## **6.11. Participant and Study Completion**

A completed participant is one who has completed all phases of the study including the follow-up visits.

The end of the study is defined as the last participant's last visit.

# **7. STUDY TREATMENT**

## **7.1. Investigational Product and Other Study Treatment**

The term study treatment is used throughout the protocol to describe RVT-1401 or placebo.

To maintain the study blind within the double-blind phase of the study, all participants will receive two injections (2 ml volume each) by an unblinded designee (Section 7.6); participants receiving the 680 mg dose will receive two injections of RVT-1401, while participants receiving the 340 mg dose will receive one injection with RVT-1401 and one

placebo injection. Participants receiving placebo will receive two injections of placebo. The blinded syringes will be numbered so that any injection site reaction can be assigned to a specific syringe number and medication #.

The OLE is open-label. Each participant will receive 3 additional doses of RVT-1401, once every 2 weeks, as a single 340 mg injection over a 6-week period.

#### **Double-Blind: Investigational Product**

Study Treatment Name:	RVT-1401	Placebo
Supplier:		
Dosage formulation:	Sterile solution for injection.	Sterile solution for injection.
Unit dose strength(s)/Dosage level(s):	340 mg: 2mL RVT-1401 in one syringe and 2mLs placebo in the second syringe for a total of 4 mL  680 mg: 2 mL RVT-1401 in two syringes for a total of 4 mL	2 mL placebo in two syringes for a total of 4 mL
Route of Administration	SC injection	
Dosing instructions:	The detailed methods are indicated in the Pharmacy Manual. Participants will be closely monitored for reactions for up to 1 hr post-dose before they leave the clinic.	
Dose Preparation	The preparation procedure and expiry details will be included in the Pharmacy manual/product label.	

#### **OLE: Investigational Product**

Study Treatment Name:	RVT-1401
Supplier:	
Dosage formulation:	Sterile solution for injection.
Unit dose strength(s)/Dosage level(s):	340 mg: 2mL RVT-1401 in one syringe
Route of Administration	SC injection
Dosing instructions:	The detailed methods are indicated in the Pharmacy Manual. Participants will be closely monitored for reactions for up to 1 hr post-dose before they leave the clinic.
Dose Preparation	The preparation procedure and expiry details will be included in the Pharmacy manual/product label.

## 7.2. Treatment Assignment

Randomization within the double-blind phase will occur centrally using an interactive web response system (IWRS) using central randomization. Participants will be assigned in accordance with the randomization schedule, prepared prior to the start of the study. The OLE is open-label.

## 7.3. Blinding

This will be a double-blind study. The investigator and study site will also remain blinded to the IgG, albumin, total protein, alkaline phosphatase (ALP), and anti-AChR antibody data post screening as this could potentially unblind them. An unblinded Medical Monitor will review this lab data on an ongoing basis for safety. In order to maintain the blind of which treatment subjects received during the double-blind phase of the study, these labs will continue to be blinded to the investigator and study site in the OLE.

The following will apply throughout the study:

- The Investigator or treating physician may unblind a participant's treatment assignment **only in the case of an emergency** OR in the event of a serious medical condition when knowledge of the study treatment is essential for the appropriate clinical management or welfare of the participant as judged by the Investigator. Emergency unblinding will be available via the IWRS or via the unblinded pharmacist.
- The Investigator should make every effort to first contact the Medical Monitor or appropriate study personnel to discuss options **before** unblinding the participant's treatment assignment.
- If the Medical Monitor is not contacted before the unblinding, the Investigator must notify the Sponsor as soon as possible after unblinding.
- The date and reason for the unblinding (the event or condition which led to the unblinding) must be fully documented in the eCRF

A participant will be withdrawn if the participant's treatment code is unblinded by the Investigator or treating physician.

The Sponsor or their designee may unblind the treatment assignment for any participant with a SAE. If the SAE requires that an expedited regulatory report be sent to one or more regulatory agencies, a copy of the report, identifying the participant's treatment assignment, may be sent to Investigator in accordance with local regulations.

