To ensure robustness of analysis conclusions against parametric assumptions, rank analogues will be executed as sensitivity analysis. If the PPS differs from the FAS by more than 10%, the analyses will be replicated on the PPS. If the PPS and the FAS do not differ by more than 10%, analysis may not be done on the PPS. Final judgments will be made at the blinded data review meeting in accordance with ICH E9.

All analyses will be done using the intent-to-treat (ITT) principle.

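### Mandatory withdrawal after an investigator code break ends scheduled assessments, so a Week 7 IgG value that could be observed is carried forward or imputed instead

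*Protocol*

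**What the plan says.** Protocol 7.3 is categorical: a participant whose "treatment code is unblinded by the Investigator or treating physician" must be withdrawn. The investigator may break the code only in an emergency or "in the event of a serious medical condition when knowledge of the study treatment is essential" to managing the participant.

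Section 7.3 does not say what the participant is withdrawn from. Section 6.8.1 lists the circumstances in which the investigator "may discontinue/withdraw a study participant's participation in the study if any of the following criteria apply". That refers to the study, but a code break is not on the list. Section 6.8.1 adds: "If a participant meets a withdrawal criterion during treatment, an Early Termination visit will be required". Section 6.8.2 says that "the Principal Investigator must make every effort to perform an Early Termination Visit" for anyone discontinued early. Neither document provides for scheduled visits after that.

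Section 7.3 also states: "The investigator and study site will also remain blinded to the IgG, albumin, total protein, alkaline phosphatase (ALP), and anti-AChR antibody data post screening". The primary efficacy endpoint is percentage change in total IgG at Week 7 (SAP 9.1), and IgG is in the central-laboratory panel (Protocol 8.4.4). SAP 9.3 says: "All analyses will be done using the intent-to-treat (ITT) principle".

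SAP 6.3 gives, as an example of a possible major deviation, a randomized subject who met withdrawal criteria but stayed in the study.

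**The concern.** The rule ties the end of data collection to an event that is itself tied to clinical outcome. Code breaks occur only in emergencies or serious conditions, so any missing Week 7 values they cause may be informative. The primary variable could still be measured after the break, in a central laboratory, with the result hidden from the site.

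An analysis that claims the ITT principle should prefer the observed value to a modelled one. Safety is also a primary objective. Protocol 3.3.1 relies on scheduled IgG and albumin monitoring by an unblinded Medical Monitor for two named risks, and that schedule would end in a participant who has just had a serious problem. With about seven participants per arm, one such case is visible.

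**Working it through.** **What happens to the data after a code break**

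| Question | Where | Answer |
|---|---|---|
| Are data already collected dropped? | SAP 5.1 | No. The SAF keeps every dosed subject. The FAS keeps randomized, dosed subjects with one valid post-treatment value, and dropouts remain in it. The PD set needs a dose, a baseline and one post-baseline value. |
| Is there a closing assessment? | Protocol 6.8.1, 6.8.2 | Yes, an Early Termination visit. From the copy of the visit tables available I could not confirm whether total IgG is drawn there. |
| Are adverse events followed? | Protocol 11.7 | Yes, reported events are followed until they resolve or stabilize, or the participant is lost to follow-up. |
| Are later scheduled IgG, albumin and safety assessments made? | Protocol 6.8, 8.1, 8.2 | None is provided for, if withdrawal means the study. |
| What stands in for a missing Week 7 IgG? | SAP 5.5, 9.3 | One subject missing: the most recent value. More than one: multiple imputation, with LOCF as sensitivity analysis. |
| Is unblinding an intercurrent event? | SAP 8 | It is not named. |

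**Why a substitute is not equivalent.** Protocol 3.2.2 expects the IgG nadir by the fifth dose, then a return to baseline over 6 to 8 weeks after the sixth. A value carried forward from early treatment is therefore not a Week 7 value. The imputation model uses earlier outcomes, treatment, age, sex, disease duration, concomitant medication and baseline. It has no term for the emergency or the code break.

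**The plan's own figure.** Inputs from Protocol 10.1: 33-point difference, SD 20, two-sided alpha 0.05, z-test, 90% power. Allocation is 1:1:1 with 21 participants, so 7 per arm.

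Power = Φ(Δ/SE − 1.960), with SE = 20 × √(1/n₁ + 1/n₂).

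- 7 vs 7: SE = 10.69; 33/10.69 = 3.087; Φ(1.127) = 87.0%.

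The stated 90% is not reproduced. Pooling the active arms (14 vs 7) gives 94.6%. That is a separate matter and neither supports nor weakens this point.

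**If Week 7 values were lost outright** (the number lost is an assumption; the documents give no rate). Detectable difference at 90% power = (1.960 + 1.282) × SE.

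- 7 vs 7: 3.242 × 20 × √(1/7 + 1/7) = 34.7 points.
- 6 vs 7: 3.242 × 20 × √(1/6 + 1/7) = 36.1 points.

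Power at 33 points:

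| Week 7 values available | Power |
|---|---|
| 7 vs 7 | 87.0% |
| 6 vs 7 | 84.3% |
| 6 vs 6 | 81.5% |

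These rows assume deletion, which the SAP does not do, so they bound the information lost. They do not measure bias. Before covariate adjustment, an error of *e* points in one substituted value moves the mean of an arm of 7 by *e*/7. The documents give no basis for sizing *e*.

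**The case against.** The case against rests mainly on safeguards elsewhere in the documents.

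- A reader might infer that the rule discards valid IgG and safety data. It does not: neither document excludes data because a code was broken, and the Early Termination visit and event follow-up remain. What stops is further scheduled collection. Event follow-up covers events already reported; it does not replace the scheduled laboratory tests that would detect new ones.
- A reader might infer that the participants lost are exactly those with serious events. Section 7.3 also lets the sponsor unblind a participant with an SAE, and send the investigator a report naming the treatment, with no withdrawal attached. The rule covers one route only.
- A reader might infer that knowing the arm cannot affect IgG because the site never sees the result. That protects the measurement, not the care given. The code is broken to guide management, and SAP 10.4 anticipates IVIG or plasma exchange as rescue. This objection stands, and the sensitivity display must therefore include the laboratory endpoints.
- Section 7.3 never says withdrawn from the study. That is also right. Study withdrawal is the reading that fits 6.8.1, but the wording is ambiguous.
- The event looks rare. SAP 4 reports no unblinding when the SAP was finalized, and SAP 2 reports no study withdrawals at blind data review. Protocol 6.1 also allows replacement. These facts limit the likely size of the problem, but they do not rule out a later code break, and a replacement does not restore the missing value.

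**Conclusion.** The point holds in limited form. If withdrawal means leaving the study, a code break before Week 7 replaces an observable, site-masked primary value with a carried-forward or imputed one, in a participant selected by an emergency. Later scheduled IgG, albumin and safety assessments also end. A code break after Week 7 leaves the primary value intact and costs only later follow-up.

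For one affected participant the precision cost is at most a move from 34.7 to 36.1 points in detectable difference, or from 87.0% to 84.3% power at 33 points, assuming SD 20 and a two-sided z-test. The possible bias cannot be sized from the documents. The frequency is unknown, and may be zero. This is an inexpensive improvement to the plan and does not threaten its main conclusion.

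**What to change.** 1. **Protocol 7.3 and 6.8.1.** State whether withdrawal after a code break refers to study treatment or to the study, and make the two sections agree. The effect on dosing is for the sponsor to reconcile between these passages; no view is offered here.
2. **Protocol 7.3.** Record and flag a code break, and say that it does not by itself end scheduled PD, PK and safety assessments through Week 18.
3. **SAP 5.1 and 6.3.** Say that such a participant stays in the FAS, and that remaining on the visit schedule after a code break is not a major deviation. Otherwise SAP 6.3 could penalize the retention that item 2 asks for.
4. **SAP 8.** Name the code break as an intercurrent event and say how it is handled.
5. **SAP 9 and 12.** Show IgG, anti-AChR and MG-scale results with and without post-unblinding values, because treatment may change once the arm is known.

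The cost is a wording amendment, a few extra displays, and visits on the existing schedule that would otherwise stop. The downside is that MG-scale values after unblinding are no longer masked, which is why item 5 is needed.

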## 7.4. Packaging and Labeling

RVT-1401 will be supplied to the study site as a sterile liquid formulation with a nominal fill of at least 1 mL in Nuova Ompi 2R clear glass vials with a flip-off cap. The solution is clear to slightly yellow, essentially free of visible particles, for SC administration. ■■■

Placebo will be provided as a sterile liquid formulation with at least a 1 mL fill in Nuova Ompi 2R clear glass vials with a flip-off cap. The solution is clear, essentially free of visible particles, for SC administration.

Doses will be prepared by the unblinded pharmacist or designee with a label that includes at a minimum the study number, participant number, medication number and vial number. Doses are administered to participants by pre-identified unblinded clinic staff or designee.

See Pharmacy Manual for exact instructions on dose preparation.

All labels will meet all local applicable requirements and Annex 13 of Good Manufacturing Practices: Manufacture of investigational medicinal products (July 2010) and/or other local regulations as applicable.

